6.4.1. General Medical History

Data for general medical history will be presented in a listing.

6.4.2. Disease-Specific History

The number and percentage of subjects exposed to prophylactic HPV vaccine will be summarized. For the subjects who had a prior CIN diagnosis the following will be summarized: CIN grade, received prior treatment (Y/N), and time from initial diagnosis. For the subjects who had prior treatment, the type of last treatment and time from the last treatment will be summarized. Time from the most recent Pap smear prior to screening and results will also be summarized.

Time from initial diagnosis = date of randomization- date of initial diagnosis.

Time from the last treatment = date of randomization- date of the last treatment.

Time from the most recent Pap smear = date of randomization- date of the most recent pap smear.

These calculations will be done only when the dates are available, and no imputation is applied for these missing dates.

7. Treatments and Medications

7.1.Prior and Concomitant Medications

For the purpose of inclusion in prior and/or concomitant medication summaries, incomplete medication stop dates will be imputed; start dates will not be imputed.

Missing stop dates will be handled as follows (where UK, UKN and UNKN indicate unknown or missing day, month and year respectively):

- UK-MMM-YYYY: impute to the last day of the month;
- DD-UNK-YYYY: impute to DD-DEC-YYYY;

- DD-MMM-UNKN: impute to DD-MMM-YOLV, where YOLV is year of subject's last study visit;
- UK-UKN-YYYY: impute to 31-DEC-YYYY;
- UK-MMM-UNKN: impute to LD-MMM-YOLV, where LD is the last day of MMM and YOLV is year of subject's last study visit;
- DD-UNK-UNKN: impute to DD-DEC-YOLV, where YOLV is year of subject's last study visit;
- UK-UKN-UNKN: impute to day of subject's last study visit.

If the imputed stop date is before the raw start date, then the imputed stop date will be set as the same as the start date.

All medications will be coded according to the latest version of World Health Organization drug dictionary.

The mITT population will be used for the main summaries of medication. If there are subjects who are included in ITT population but not the mITT population for medications, which will consist of those who are randomized but never dosed, then their medication data will be summarized separately and always considered to be prior medication by definition.

7.1.1. **Prior Medications**

A prior medication is defined as any medication that has a stop date before the first dose of study drug (prior to Day 1). The number and percentage of subjects with at least one prior medication will be summarized by treatment arm. The number and percentage of subjects with each prior medication will be summarized by treatment arm and by drug class and preferred term.

Summaries will be performed on the baseline biomarker-positive subjects and on all subjects (regardless of biomarker status) separately. Listings will flag all subjects who are baseline biomarker positive.

7.1.2. Concomitant Medications

A concomitant medication is defined as any medication that has a stop date that is on or after the date of first dose of study drug. The number and percentage of subjects with at least one concomitant medication will be summarized by treatment arm. The number and percentage of subjects with each concomitant medication will be summarized by treatment arm and by drug class and preferred term.

Summaries will be performed on the baseline biomarker-positive subjects and on all subjects (regardless of biomarker status) separately. Listings will flag all subjects who are baseline biomarker positive.

7.2.Study Treatments

Number of doses taken and percentage of subjects at number of doses will be summarized by the treatment arm. Furthermore, the number and percentage of total number of device attempts made and reasons for non-success will be summarized by the treatment arm. The ITT population will be used for these summaries. Listings will present relevant device details.

Summaries will be performed on the baseline biomarker-positive subjects and on all subjects (regardless of biomarker status) separately. Listings will flag all subjects who are baseline biomarker positive.

8. Efficacy and Immunogenicity Analysis

8.1. Efficacy Analyses

All of the efficacy endpoints analyses will use the ITT population. Analyses of primary and secondary efficacy endpoints with the mITT and PP populations will be considered supportive of the corresponding ITT population. Analyses will be performed on the baseline biomarker-positive subjects and on all subjects (regardless of biomarker status) separately. Listings will flag all subjects who are baseline biomarker positive.

Subgroup analysis of the primary and secondary efficacy endpoints will also be conducted by history of exposure to prophylactic HPV vaccines.

8.1.1. Primary Efficacy Endpoint

The primary efficacy endpoint is the proportion of baseline biomarker-positive subjects with no evidence of cervical HSIL (i.e., no evidence of CIN2, CIN3) on histology sample and no evidence of HPV-16 and/or HPV-18 in cervical samples by type specific HPV testing at the Week 36 timeframe.

The primary hypothesis of superiority is:

H₀: $\delta \leq 0$ vs. H₁: $\delta > 0$,

where $\delta = Pv - Pp$, and Pv and Pp denote the true biomarker-positive population probabilities of the primary endpoint for VGX-3100 and Placebo, respectively. The proportion in each treatment arm is calculated by the number of responders divided by the total number of responders and non-responders in the study population of the corresponding treatment arm. The detailed definitions of responder and non-responder are listed in Table 1.

For the primary endpoint, week 36 histology is evaluated based on the first biopsy or surgical excision procedure on or after Day 238; in case of multiple results on the same day, the one with worst grade will be used. The virology results used for analysis must be the latest result that is on or before the same date as the histology result and is taken on or after Day 238. If

a subject undergoes excision or cervical biopsy at any time on or after Day 1 and before Day 238, the subject will be considered as non-responder. Number of responders and non-responders, proportion of responders in each treatment arm, and difference of proportions between the two treatment arms will be presented. A p-value of superiority based on a test of risk difference and corresponding 95% confidence interval using the method of Miettinen and Nurminen [5] will be computed. Superiority will be concluded if the one-sided p-value is <0.025 and the corresponding lower bound of the 95% CI exceeds zero.

Responder proportion will also be summarized based on the stratification factors separately.

Responder	Non-Responder
Subject with no histologic evidence of cervical HSIL ^a at Week 36 evaluation and no evidence of HPV-16 and/or HPV-18 at Week 36 ^b AND Subject in which an excision or biopsy sample ^c was NOT obtained between initial dose up to Week 36	Subject with histologic evidence of cervical HSIL, Adenocarcinoma-in-situ (AIS), cervical carcinoma at Week 36 OR Subject with evidence of HPV-16 or HPV-18 at Week 36 OR Subject in which an excision or biopsy sample was obtained between initial dose up to Week 36 OR Subjects with no Week 36 sample result

Table 1. Definition of Primary Endpoint Responder and Non-Responder

a. No evidence of HSIL is defined by histology as negative, squamous atypia, or LSIL

b. The histopathologic efficacy time frame is defined by those who have undergone a biopsy or surgical excision at any time starting from 14 days prior to the protocol-specified target date of Week 36. The first tissue removal sample in this time frame determines the histology endpoint. The most recent HPV clearance result prior to tissue removal, which includes results from the same date, within the time frame determines the HPV clearance endpoint.

c. Excludes ECC-only samples

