Protocol Title: REVEAL 2, A Prospective, Randomized, Double-blind, Placebo-Controlled Phase 3 Study of VGX-3100 Delivered Intramuscularly (IM) followed by Electroporation with CELLECTRATM 5PSP for the Treatment of HPV-16 and/or HPV-18 related High Grade Squamous Intraepithelial Lesion (HSIL)¹ of the Cervix

Protocol Number: HPV-303

Trial Phase: 3

Estimated Number of Trial Centers and Countries/Regions: Approximately 50 study centers in approximately 9 countries

Formulation: VGX-3100 delivered with CELLECTRATM 5PSP Electroporation Device

Trial design: Prospective, Randomized, Double-blind, Placebo-Controlled

Criteria for evaluation:

Hypothesis: Among baseline biomarker-positive women, three 6 mg doses of VGX-3100 (DNA Plasmids encoding E6 and E7 proteins of HPV-16 and HP -18) livered by intramuscular (IM) injection followed by electroporation (EP) with CELLE $\pi RA^{TM} 5P_{-}$ to adult women with histologically confirmed high-grade squamous intraepi helial lesions (HSIL), Cervical Intraepithelial Neoplasia, (CIN2, CIN3) of the cervix, associated with HPV-16 and/or HPV-18 will result in a higher percentage of women with histopathological regression of cervical (HSIL) lesions to no evidence of cervical HSIL and virologic clearance of HPV-16 and/or HPV-18 compared to placebo delivered IM followed by EP with CELLECTRATM 5PSP at the Week 36 visit.²

Primary Objective: Among baseline biomarker-positive wom'n, determine the efficacy of VGX-3100 compared with placebo with respect to combined histopatho¹ gic regression of cervical HSIL and virologic clearance of HPV-16 and/or HPV-18.

Primary Endpoint: Proportion of baseline bio. arker-positive women with no evidence of cervical HSIL on histology sample and no evidence of HPV-16 and/or HPV-18 in cervical samples by type specific HPV testing at Week 36 visit.

 2 The time frame is defined as any time starting from 14 days prior to the protocol-specified target date of Week 36.

Version Date: 01Jun2022

CONFIDENTIAL

Version 4.1

Page 13 of 87

Downloaded by

¹ Terminology based on 2012 consensus recommendation on Lower Anogenital Squamous Terminology (LAST) from the American Society of Colposcopy and Cervical Pathology (ASCCP) and the College of American Pathologists (CAP)

Secondary Objectives	Associated Secondary Endpoints

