6.1.2 STUDY EVALUATIONS AND PROCEDURES

Once eligibility has been confirmed, the subject will be randomized to receive study treatment. Visit dates and windows must be calculated from Day 0.

DAY 0

The following evaluations will be performed at Day 0 prior to study treatment:

- Determination of eligibility per inclusion/exclusion criteria
- Randomization .
- Targeted physical assessment •
- Vital signs including weight

Version Date: 01Jun2022

CONFIDENTIAL

Version 4.1

Page 52 of 87

Urine pregnancy test

- 2 digene[™] cervical brush samples •
- ThinPrepTM sample for HPV typing and pap smear (subject should be requested to abstain from any sexual activity and refrain from use of douching or vaginal lubricants/medication for a period of 24 hours prior to sample collection)
- Oropharynx (OP) sample by oral rinse and vaginal swabs for HPV testing
- Intra-anal swab (if subject has consented to intra-anal sampling) for HPV testing
- Colposcopy
- Study treatment administration

The following evaluations will be performed on Day 0 post-t eatment:

- Post treatment adverse event and injection site reactio asses ment at least 30 minutes after study treatment
- Distribute Participant Diary Card (PDC)

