4.5. Baseline Definition

Baseline is defined as the last measurement prior to the first treatment administration. If the first treatment date is not available, the last measurement before or on the randomization date will be used.

4.6.Study Day

The day of the first study treatment is defined as Day 1. Study day for a particular event date is calculated as (Date of event – Date of Day 1 + 1) if the event occurs on or after Day 1, or (Date of event – Date of Day 1) if the event occurs prior to Day 1, and the study day of any event prior to the first study treatment will be a negative number. Duration of an event will be calculated as (Event end date – Event start date +1).

5. Subject Disposition

5.1.Disposition

Number and percentage of subjects in each analysis population will be summarized by treatment arm and total.

Additionally, the number and percentage of subjects who received each dose, complete all electroporation/study treatments, completed all study visits, discontinued study treatment, and early withdraw from the study will be presented. The reasons for study treatment discontinuation and early withdrawal from study will also be summarized.

A disposition table of subjects by country and site, and by treatment will also be summarized.

Summaries will be performed on the baseline biomarker-positive subjects and on all subjects (regardless of biomarker status) separately. Disposition listings will flag all subjects who are baseline biomarker positive.

5.2.Protocol Deviations

Deviations from the protocol including violations of inclusion/exclusion criteria will be identified in cooperation with the sponsor. All subjects excluded from the PP population will also be identified. These identifications will be defined prior to database lock.

Protocol deviations are to be mainly classified as a ICH-GCP/non-ICH GCP deviation as well as a Covid/Non-Covid Related deviation. In addition, the number and percentage of subjects with at least one protocol deviation, 1 deviation, 2 deviations, >2 deviations will be summarized. Subjects excluded from the PP population will be presented separately.

6. Demographics and Baseline Characteristics

6.1.Demographics

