8.1.2. Secondary Efficacy Endpoints

For the secondary efficacy endpoints listed in Section 3.2.2 of this SAP, the analysis method will be the same as for the primary endpoint described in Section 8.1.1, but without p-values.

In addition, the definition of responder and non-responder for each endpoint is defined in Table 2.

Final Statistical Analysis Plan, Version 1.2 Date Issued: 310CT2022

Table 2. Definition of Secondary Endpoints Responder and Non-Responder

Endpoint	Responder	Non-Responder				
Proportion of subjects with no evidence of cervical HSIL on	Subject with no histologic evidence of cervical HSIL ^a at Week 36 ^b	Subject with histologic evidence of cervical HSIL, AIS, cervical carcinoma at Week 36				
histology sample at Week 36 visit	AND	OR				
	Subject in which an excision or biopsy sample ^c was NOT obtained between initial dose up to	Subject in which an excision or biopsy sample was obtained between initial dose up to Week 36				
	Week 36	OR				
		Subjects with no Week 36 sample result				
Proportion of subjects with no evidence of HPV-16 and/or	Subject with no evidence of HPV-16 and/or HPV-18 ^d at Week 36	Subject with evidence of HPV-16 or HPV-18 at Week 36				
HPV-18 in cervical samples by type specific HPV testing at Week 36 visit	AND Subject in which an excision or biopsy sample was	Subject in which an excision or biopsy sample was obtained between initial dose up to Week 36				
	NOT obtained between initial dose up to Week 36	OR				
		Subjects with no Week 36 sample result				
Proportion of subjects with no evidence of squamous atypia,	Subject with no histologic evidence of cervical HSIL, squamous atypia, or LSIL ^e at Week 36	Subject with histologic evidence of cervical HSIL, squamous atypia, LSIL, AIS, cervical carcinoma at Week 36				
LSIL, or HSIL on histology sample at Week 36 visit	AND	OR				
	Subject in which an excision or biopsy sample was NOT obtained between initial dose up to Week 36	Subject in which an excision or biopsy sample was obtained between initial dose up to Week 36				
		OR				
		Subjects with no Week 36 sample result				

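### SAP 8.1.1 opens the Week 36 efficacy window at Day 238, but under the SAP's own day numbering the stated 14-day rule gives Day 239

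*SAP*

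**What the plan says.** **Numbering.** SAP 4.6 (Study Day): "The day of the first study treatment is defined as Day 1". For events on or after first treatment it adds 1 to the date difference, so the SAP's study-day scale has no Day 0. The protocol labels the first-treatment day Day 0 (5.4) and says in 6.1.2 that "windows must be calculated from Day 0". Protocol 3.5 places the primary endpoint 36 weeks after the first dose.

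**The window in words.** SAP Table 1 note b accepts a biopsy or excision "at any time starting from 14 days prior to the protocol-specified target date of Week 36". Protocol Table 4 note b and Protocol 8.5.1 state the same rule. The protocol synopsis, footnote 2, says: "The time frame is defined as any time starting from 14 days prior to the protocol-specified target date of Week 36".

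**The window as a day number.** SAP 8.1.1 uses Day 238 three times:
- Histology: "week 36 histology is evaluated based on the first biopsy or surgical excision procedure on or after Day 238".
- Virology: the HPV result must be "the latest result that is on or before the same date as the histology result and is taken on or after Day 238".
- Early tissue: a woman is a non-responder if "a subject undergoes excision or cervical biopsy at any time on or after Day 1 and before Day 238".

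**Secondary endpoints.** SAP 8.1.2 says that "the analysis method will be the same as for the primary endpoint" and sends the reader to Table 2 for the responder definitions. Table 2 note b repeats the 14-day rule without a day number.

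**The concern.** SAP 8.1.1 and the note to its own table give two different calendar dates for the start of the window. Two programmers, one working from the text and one from note b, would not always classify the same woman alike. The threshold sits in the responder definition for the trial's only formal hypothesis test. It also separates two opposite treatments of the same tissue sample: on one side of the line the tissue is the endpoint, and on the other it is an early intervention that makes the woman a failure whatever follows.

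**Working it through.** **Inputs**
- First dose: Day 0 in the protocol (5.4), Day 1 in the SAP (4.6).
- Week 36 target: 36 weeks after first dose (Protocol 3.5, 6.1.2).
- Window opens 14 days before target (SAP Table 1 note b; Protocol Table 4 note b, 8.5.1).
- Visit windows: Week 36 ± 1 week and Week 28 ± 1 week (Protocol Table 1).

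**Step 1: reproduce 238.** Target = 36 × 7 = 252 days after first dose. Opening = 252 − 14 = 238 days after first dose. With the first dose as Day 0 this is Day 238, the figure in the SAP.

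**Step 2: apply the SAP's numbering.** Study day = (event date − first-dose date) + 1.

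| | Days after first dose | Protocol day | SAP day |
|---|---|---|---|
| Week 36 target | 252 | 252 | 253 |
| Window opens (14-day rule) | 238 | 238 | 239 |
| SAP Day 238 as written | 237 | 237 | 238 |

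SAP Day 238 is 253 − 238 = 15 days before target. Calling the target SAP Day 252 would give 252 − 14 = 238, but SAP Day 252 is only 251 days after first dose, which is not 36 weeks.

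**Step 3: who is affected.** Only a sample dated exactly SAP Day 238 is treated differently. The Week 36 visit window is 253 ± 7 = Days 246 to 260, so Day 238 falls 246 − 238 = 8 days before it opens. The latest on-schedule Week 28 visit is 1 + 196 + 7 = Day 204. No scheduled sample falls on Day 238.

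**Step 4: direction in the primary ITT composite analysis.** Missing data count as failures.
- *Tissue on Day 238.* With cut-off 239 it is early tissue, so the woman is a non-responder regardless. With cut-off 238 it is endpoint tissue, so she may be a responder.
- *No tissue on Day 238, but the deciding HPV sample is on Day 238.* With cut-off 239 there is no qualifying HPV result, so she is a non-responder. With cut-off 238 a negative result can make her a responder.
- *Anything else.* Both cut-offs give the same status.

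Any change is therefore from non-responder (239) to responder (238).

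**Step 5: direction in the per-protocol sensitivity analysis.** Protocol 8.5.1 and SAP 4.3.3 add an analysis that uses the Week 36 time-frame result regardless of earlier procedures. Take a woman in that population with HSIL tissue on Day 238, then tissue without HSIL and a negative HPV-16/18 sample on Day 253. With cut-off 238 the first tissue in the window is the Day 238 sample, so she is a non-responder. With cut-off 239 that sample is ignored and Day 253 decides, so she is a responder. The direction is reversed.

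**The case against.** The strongest reply is that 238 is correct in the protocol's numbering, that the SAP itself still uses Day 0 for visits (SAP 4.2, 3.3 and the schedule in Appendix 13.1), and that note b states the intended rule correctly. On that view this is a missing shift of one in a label, with no scheduled sample near it. The account of how it arose is plausible, and the point about size stands. It does not rescue the text. The early-tissue sentence in SAP 8.1.1 starts its own count at Day 1, so the Day 238 beside it cannot be read on a Day 0 scale. Nor is a deliberate widening to 15 days documented: SAP Section 11, on changes to the planned analysis, lists only the medical-history summaries.

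Three stronger readings are tempting, and the documents do not support them.
- *That the error always favours response.* This holds for the primary ITT composite only; step 5 gives a pre-specified analysis where it reverses.
- *That the secondary endpoints are certainly affected.* The histology sentence in SAP 8.1.1 is limited to the primary endpoint, and Table 2 note b already states the 14-day rule. SAP 8.1.2 may carry Day 238 over, but that is an inference.
- *That the cut-off for early tissue is undefined*, because some protocol and table text runs it up to the Week 36 visit and other text to the start of the time frame. The footnotes and the analysis sections (Protocol 8.5.1, 8.5.9; SAP 4.3.1) settle the intended reading. That difference is editorial and separate from the day count.

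**Conclusion.** The point holds and is minor. SAP 8.1.1 is wrong as written by one calendar day at three places in the primary responder rule, and it contradicts SAP Table 1 note b. The documents show no misclassified woman and give no count of samples on Day 238, so nothing here suggests that the trial's result would change. The sample size and power statements do not use this threshold. It is still worth correcting, because the error is certain, lies in the decision rule for the only hypothesis test and, in that analysis, can only add responders.

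The conclusion assumes that the 14-day rule is the intended one, that SAP 4.6 governs the day numbers in SAP 8.1.1, and that the Week 36 target is counted from the first dose. The per-protocol example also assumes that the Day 238 biopsy does not itself exclude the woman from that population.

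**What to change.** Before unblinding, in SAP 8.1.1:

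1. Replace Day 238 with Day 239 in all three places (histology, virology, early tissue), or define the cut-off once as first-dose date + 238 days. The second form does not depend on how the first day is numbered.
2. State in SAP 8.1.2 that the same cut-off applies to the tissue-based and cervical-HPV-based secondary endpoints.

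The rules on first tissue in the window and on HPV sampling on or before tissue removal stay as they are. The cost is one constant in the endpoint program and a short SAP revision. The correction needs no new data, visits or patients and no change to the protocol text, which already states the rule correctly.

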A Data Safety Monitoring Board (DSMB) will also advise the Sponsor if it appears that the frequency of regression in the VGX-3100 group is unacceptably low compared to the placebo group. These measures should minimize the risk of progression of the cervical HSIL and the risk of harboring an undiagnosed occult early invasive cervical cancer. Secondary to the potential risk of progression to cancer during the course of the trial described above, all subjects with the suggestion of residual disease will undergo excisional therapy (e.g. CKC, LEEP, LLETZ) at Week 36 as part of the efficacy assessment. In the HPV-003 study, the percentage of subjects with micro-invasive cancer found in larger surgical excision samples in subjects who had no evidence of invasive cancer by initial biopsy was 1.8%, (2/114 with specimens), which is consistent with that reported under standard of care settings [17]; never the less, all subjects will undergo excision at Week 36 to ensure no evidence of occult progression.

Version Date: 01Jun2022

CONFIDENTIAL

Version 4.1

Page 25 of 87

Downloaded by

For further information concerning the risks associated with VGX-3100 and the CELLECTRA[™] 5PSP device please refer to the User Manual and the Investigator's Brochure.

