6.4.15 UNSCHEDULED BIOPSIES

In the event an unscheduled biopsy is performed prior to the Week 36 visit, the subject will be classified as a non-responder in the efficacy analyses. The subject may discontinue further study treatment and continue in the study for safety follow-up visits. The subject will be managed according to standard of care and the investigator's judgment based on the results of the histological diagnosis from the unscheduled biopsy. Additional instructions for collecting ectocervical biopsies are detailed in Appendix A. All biopsy samples/excised tissue will be sent to the central pathology lab for review by PAC.

Version Date: 01Jun2022

CONFIDENTIAL

Version 4.1

Page 59 of 87

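### A clean off-schedule biopsy on or after Day 238 fixes Week 36 histology, so HSIL or worse in a later Week 36 excision is not scored

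*SAP*

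**What the plan says.** **Histology.** SAP 8.1.1 states that "week 36 histology is evaluated based on the first biopsy or surgical excision procedure on or after Day 238". Table 1 note b repeats it: "The first tissue removal sample in this time frame determines the histology endpoint". The only worst-grade provision is narrower: "in case of multiple results on the same day, the one with worst grade will be used". Table 2 note a of the SAP and the footnotes to Protocol Tables 4 to 8 carry the same first-sample rule, so it also governs regression, complete regression and non-progression.

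**Virology.** "The virology results used for analysis must be the latest result that is on or before the same date as the histology result", and it must also have been taken on or after Day 238.

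**Earlier tissue.** Under SAP 8.1.1, when a woman "undergoes excision or cervical biopsy at any time on or after Day 1 and before Day 238, the subject will be considered as non-responder". The time frame is described as "starting from 14 days prior to the protocol-specified target date of Week 36".

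**Planned tissue.** Protocol 3.1.2 and 3.2.1 obtain the regression specimen by excision at Week 36. Sections 1.4.1 and 3.5 send all women to excision. Protocol Table 1 lists ectocervical biopsy at Screening only.

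**Other protocol wording on earlier tissue.** Section 6.4.15 provides that if "an unscheduled biopsy is performed prior to the Week 36 visit, the subject will be classified as a non-responder". Section 6.4.14 and a bullet in 3.1.4 say much the same, by reference to the Week 36 visit or evaluation.

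**The concern.** The endpoint is absence of HSIL, and the protocol names the Week 36 excision as the tissue that decides it. The scoring rule lets a smaller sample taken earlier in the time frame displace that excision, and nothing brings a later, worse reading back. Investigators are told to biopsy when they suspect progression (Protocol 3.5, 6.4.14, 7.1), so the women exposed to the rule are those in whom disease was suspected.

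At stake is what the regression and non-progression rates mean and, for a smaller group, the primary response rate. A second issue is that an unscheduled biopsy inside the time frame but before the Week 36 visit is scored differently depending on which section is read.

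**Working it through.** **1. Calendar.** SAP 4.6 makes the first dose Day 1.
- Week 36 target: 36 × 7 + 1 = Day 253. The visit window of ±1 week is Day 246 to 260.
- Week 28 target: 28 × 7 + 1 = Day 197. Its window ends on Day 204.
- Fourteen days before target is 253 − 14 = Day 239. Day 238 fits only if the first dose is Day 0 (252 − 14 = 238). This is a one-day mismatch.
- A biopsy on Day 238 to 245 is therefore inside the SAP time frame but before the visit window.

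**2. Two illustrative women, neither with tissue taken before Day 238.**

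| | Woman A | Woman B |
|---|---|---|
| Off-schedule biopsy | Day 242, normal | Day 253 (Week 36 visit), normal |
| HPV-16/18 sample | Day 253, negative | Day 253, negative |
| Excision | Day 253, HSIL | Day 259, HSIL |
| Histology used by the SAP | Day 242, normal | Day 253, normal |
| Qualifying HPV result | None: it must fall on Day 238–242 | Day 253, negative |
| Histology-only endpoints (SAP) | Regressed, not progressed | Regressed, not progressed |
| Primary endpoint, ITT (SAP) | Non-responder (no valid virology) | Responder |
| Protocol 6.4.15 | Non-responder | Not reached: biopsy was at the visit |

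HPV samples are scheduled at Week 28 (latest Day 204) and then Week 36 (earliest Day 246). Woman A therefore has a qualifying result only if an extra sample was taken on Day 238–242. If biopsy and excision fall on the same day, the worst-grade rule already protects the endpoint.

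**3. Weight of one woman.** Inputs from SAP 4.1: 198 women, 2:1, 33% biomarker-positive.
- 198 × 0.33 = 65.3, or about 44 and 22. 1/44 = 2.3 points; 1/22 = 4.5 points.
- All women: 132 and 66. 1/132 = 0.8 points; 1/66 = 1.5 points.

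**4. The plan's own power** (66% vs 15%, one-sided 0.025, stated as above 90%).
- Pooled rate: (22 × 0.15 + 44 × 0.66)/66 = 0.49.
- SE under the null: √[0.49 × 0.51 × (1/22 + 1/44)] = 0.1305.
- SE under the alternative: √[0.15 × 0.85/22 + 0.66 × 0.34/44] = 0.1044.
- Power: Φ[(0.51 − 1.96 × 0.1305)/0.1044] = Φ(2.435) = 99.3%.
- Exact enumeration of the Miettinen–Nurminen test gives 98.8%. The stated figure reproduces.

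**5. Effect of rescoring.** The documents give no rate of a clean first sample followed by HSIL or worse in a later excision. The shares below are assumptions, not estimates. A share f of responders becomes non-responders, so each affected rate is multiplied by (1 − f). Power is exact, with 44 vs 22.

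| f | Both arms: difference, power | VGX-3100 only: difference, power |
|---|---|---|
| 0 | 51.0 points, 98.8% | 51.0 points, 98.8% |
| 2% | 50.0, 98.6% | 49.7, 98.4% |
| 5% | 48.5, 98.1% | 47.7, 97.6% |
| 10% | 45.9, 97.0% | 44.4, 95.6% |
| 20% | 40.8, 93.6% | 37.8, 87.9% |

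Only the last VGX-3100-only case falls below 90%. It would need 44 × 0.66 × 0.20 = about 6 such women in that arm, each with an off-schedule biopsy.

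**6. Planned sensitivity analyses.** The additional per-protocol analysis (Protocol 8.5.1, SAP 4.3.3) concerns procedures before the time frame. The mITT analysis concerns missing data. Neither uses a later in-window specimen.

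**The case against.** The best defence is that a first-sample rule has a reason. Removing tissue can itself produce apparent improvement (Protocol 3.1.4, 6.4.14), so histology and HPV status are both read at the first removal. That supports fixing HPV status there. It does not support discarding later HSIL, which cannot be artefactual improvement. It is fair to add that a worst-grade rule gives women with more specimens more chances to fail.

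The defence is also right that the path is narrow. Version 4.1 plans excision alone at Week 36. SAP Appendix 13.1 still lists a Week 36 biopsy, but as an alternative to excision.

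A reader might infer more than the documents support:
- *That a biopsy shortly before the visit creates a false primary responder.* By default it does not, because no HPV sample is scheduled between Week 28 and the Week 36 visit.
- *That the SAP contradicts the protocol on the first-sample rule.* Protocol Table 4 note b has the same rule. On earlier tissue, that note, the 3.1.4 narrative, 8.5.1 and 8.5.9 use the same time frame as the SAP. The conflict is confined to 6.4.14, 6.4.15 and the 3.1.4 bullet.
- *That the Phase 2b figure gives the rate.* Protocol 1.4.1 reports that the rate of "micro-invasive cancer found in larger surgical excision samples in subjects who had no evidence of invasive cancer by initial biopsy was 1.8" per cent (2/114). That compares the entry biopsy with a later excision. It shows that a biopsy can miss disease, not how often this path occurs.
- *That every error favours response.* This is true against a worst-grade rule. Against an excision-only standard the rule cuts both ways, since HSIL on the biopsy with a clean later excision is scored as failure.
- *That type I error or safety reporting is compromised.* If the path is equally frequent in both arms under the null, type I error is not inflated. AIS and carcinoma are still reported as SAEs (Protocol 7.10).

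**Conclusion.** The point holds in a limited form. As written, a clean in-window biopsy displaces a later Week 36 excision that shows HSIL, AIS or carcinoma. The woman is then scored as regressed and not progressed on the histology-only endpoints. She is a primary responder only if a negative HPV-16/18 result also falls on or after Day 238 and on or before the biopsy, as when the biopsy is done at the Week 36 visit and the excision days later.

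Few women are likely to be affected, and the number cannot be computed from the documents. Each one moves a biomarker-positive arm by 2.3 or 4.5 points. The sample size and stated power are not in question. The case for change is that the rule can contradict the endpoint's own definition and that no planned analysis would reveal it. The conflict between visit and time-frame wording is separate and needs settling before unblinding.

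**What to change.** - In SAP 8.1.1, SAP Tables 1 and 2 and the footnotes to Protocol Tables 4 to 8, define Week 36 histology as the worst Pathology Adjudication Committee grade across all cervical tissue taken from the opening of the time frame through the Week 36 excision.
- Keep HPV status at the last in-window result on or before the first tissue removal. This preserves the protection against artefactual clearance.
- Reconcile Protocol 6.4.14, 6.4.15 and the 3.1.4 bullet with SAP 8.1.1, Protocol 8.5.1, 8.5.9, the 3.1.4 narrative and Table 4 note b, so that an in-window biopsy before the visit is scored one way.
- In the same edit, align Day 238 with the SAP's Day 1 numbering, and bring the Week 36 biopsy entries in SAP Appendix 13.1 into line with Protocol Table 1.

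The cost is wording and one programming rule. All biopsy and excision tissue already goes to the committee (Protocol 6.4.15, 12.3), and no procedure changes. The downside of the histology change is that response rates can only stay the same or fall slightly.
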